# 2.2.2.3. Combination of JNJ-3989 and JNJ-6379 with PeglFN-α2a

PegIFN- $\alpha$ 2a is a covalent conjugate of recombinant alfa-2a interferon that is indicated for the treatment of chronic hepatitis B in adult and pediatric patients at least 3 years of age. In addition, PegIFN- $\alpha$ 2a in combination with other medicinal products is indicated for the treatment of chronic hepatitis C virus (HCV)-infection in adult and pediatric patients at least 5 years of age and not treated before. The most common adverse reactions (≥10% of participants) are anorexia, anxiety, headache, concentration impairment, dyspnea, cough, alopecia, dermatitis, pruritis, dry skin, myalgia, arthralgia, asthenia, pyrexia, and fatigue. For further information regarding PegIFN- $\alpha$ 2a, refer to the currently approved prescribing information.

Treatment with PegIFN-α2a has been associated with decreases in platelet count (common adverse reaction). In the ongoing Phase 1/2a AROHBV1001 study (see Section 2.2.2.1), no effect on platelet count has been observed in the triple combination treatment cohort 12 (JNJ-3989, JNJ-6379, and NA). Of the 84 adult chronic HBV-infected participants that received 3 subcutaneous injections of JNJ-3989, 6 participants developed grade 1 platelet reduction with no general trend towards a continuous decline. For JNJ-6379, no effect on platelet count has been observed in ongoing Phase 2a HPB2001 study (Jade) for the 189 adult chronic HBV-infected participants that were dosed with JNJ-6379.

Based on preclinical data, a potential common toxicity target organ between JNJ-6379, JNJ-3989, and PegIFN- $\alpha$ 2a is the bone marrow (see Section 2.2.1, Nonclinical Studies). Bone marrow suppression is a known side effect of PegIFN- $\alpha$ 2a (rare).

No pharmacokinetic (PK) interaction is expected between JNJ-3989 and PegIFN- $\alpha$ 2a based on the known pharmacologic profiles of JNJ-3989 and PegIFN- $\alpha$ 2a. 

At the time of protocol amendment 5 writing, no clinical data on the combination of JNJ-3989 and JNJ-6379 with PegIFN-α2a are available. Nonclinical studies to investigate the effect on platelet count decreases and on bone marrow in non-human primates (JNJ-3989) and bone marrow stem cells (JNJ-6379) were completed, and results are summarized in Section 2.2.1.3..

### 2.3. Benefit-Risk Assessment

More detailed information about the known and expected benefits and risks of JNJ-3989 and JNJ-6379 may be found in the respective IBs and their Addenda. 

For the benefit-risk evaluation of tenofovir disoproxil and PegIFN- $\alpha$ 2a refer to the respective prescribing information and Summary of Product Characteristics.

JNJ-6379 was initially part of the study intervention but has been removed as study intervention with the implementation of an urgent safety measure, as described in Protocol Amendment 6. Emerging data from the REEF-1 and REEF-2 studies resulted in an unfavorable benefit-risk balance of JNJ-6379 in combination with JNJ-3989+NA, compared to JNJ-3989+NA alone. Therefore, the Sponsor decided to discontinue treatment with JNJ-6379 in all ongoing clinical studies effective immediately. Participants who were on treatment with JNJ-6379 were contacted and requested to stop taking JNJ-6379, while continuing treatment with NA, JNJ-3989 and PegIFN-α2a (as applicable). For newly enrolled participants, JNJ-6379 was taken out of the treatment regimen. For completeness, the benefit-risk assessment for JNJ-6379 is still included in this section.

# 2.3.1. Benefits for Study Participation

### 2.3.1.1. Known Benefits

The clinical benefit of JNJ-3989 and JNJ-6379 remains to be established.

#### 2.3.1.2. Potential Benefits

Results from clinical studies with JNJ-3989, JNJ-6379, NAs, and PegIFN- $\alpha$ 2a may be useful for the development of a novel therapeutic approach for chronic HBV infection.

The combination of JNJ-6379 and JNJ-3989 on a background of an NA would target different stages of the viral life cycle. While NA treatment reduces HBV DNA to levels close to or below the LLOQ of the HBV DNA assay, HBV replication is not completely inhibited, resulting in replenishment of the cccDNA pool. The addition of JNJ-6379, which targets the HBV capsid assembly ("primary" mode of action [MoA]) and the de novo cccDNA formation ("secondary" MoA), is expected to block HBV replication more profoundly by inhibiting formation of HBV RNA and DNA containing particles, and to inhibit de novo cccDNA formation, ultimately leading to reduction in cccDNA levels/transcriptional activity and HBsAg seroclearance ("intensified viral suppression"). The addition of JNJ-3989 to an NA, or to JNJ-6379 in combination with an NA, is expected to intensify viral suppression (further) by downregulating levels of the HBV DNA precursor pgRNA. In addition, JNJ-3989 reduces levels of all viral proteins including HBsAg, which is known to interfere with the host immune response. 5,18,19 By acting on both viral replication and by reducing barriers to the host immune response, higher functional cure rates may be achieved.

The addition of short-term PegIFN- $\alpha$ 2a (12-week consolidation phase) to the regimen at a time when HBsAg is already significantly reduced or eliminated, which is assumed to be associated with potential restoration of the immune response, may lead to further improvement of the immune response (such as reactivation of NK-cells and further activation of endogenous HBV-specific T-cells) and ultimately could lead to immune control of HBV (ie, functional cure). In addition, PegIFN- $\alpha$ 2a has shown to have direct antiviral effects on HBV which could also contribute to the efficacy of the regimen. By adding short-term PegIFN- $\alpha$ 2a to the regimen, higher functional cure rates may be achieved.

Investigating the treatment regimen JNJ-3989 + PegIFN- $\alpha$ 2a + NAs with and without JNJ-6379 in this immune tolerant study population might be useful for the development of a treatment for this population that currently has no recommended treatment options.

# 2.3.2. Risks for Study Participation

#### 2.3.2.1. Known Risks

No known risks associated with JNJ-3989 or JNJ-6379 have been identified from clinical observations so far in the Phase 1 and 2 studies. Injection site reactions were identified as adverse drug reactions for JNJ-3989.

Side effect profile of PegIFN- $\alpha$ 2a is well established and includes, but is not limited to, neuropsychiatric, autoimmune, ischemic, ophthalmologic, hematological, and infectious disorders. Exacerbations of hepatitis during hepatitis B therapy are common and characterized by transient and potentially severe increases in serum ALT. Marked increases in ALT were sometimes accompanied by bilirubin elevation and other liver test abnormalities. In many, but not all cases, these disorders resolve after stopping PegIFN- $\alpha$ 2a therapy. For a full list of known risks for PegIFN- $\alpha$ 2a refer to the respective prescribing information and Summary of Product Characteristics.

### 2.3.2.2. Potential Risks

All therapies have the potential to cause adverse experiences. In addition, the discontinuation of NA treatment bares a risk of hepatitis B flares.

Patients with positive HBV DNA and positive HBsAg can always experience increases in liver transaminases which may indicate immune activation and may result in the reduction of viral parameters such as HBV DNA and/or HBsAg/HBeAg. Whether this occurs at higher frequency during or after treatment with JNJ-6379 and JNJ-3989 is not known. In this context it is also possible that the interventional treatment lead to a transition of participants to a more "immune-active" disease stage. In this case long-term NA treatment after end of study participation may be needed.

This study will be conducted in a study population that according to current treatment guidelines (EASL) does not have a general treatment indication. As discussed in Section 2.1, Study Rationale, this is mainly driven by the limited efficacy of NA treatment in patients with HBeAg positive infection and by the fact that NA treatment, once initiated, usually has to be continued lifelong. The assumption to achieve functional cure with the investigated treatment regimen would change this benefit assessment, but clinical evidence is not yet available.

Please refer to Section 2.2, Background, for details on the safety results in the studies conducted to date.

#### 2.3.2.2.1. Potential Risks for JNJ-3989

#### **ALT Elevations**

ALT elevations are considered an important potential risk for JNJ-3989. Two distinct patterns of ALT elevations have been observed in participants receiving JNJ-3989: a rapidly rising and resolving ALT elevation or a more sustained pattern of ALT elevation. The latter has been observed in HBV/HDV co-infected participants in study 73763989HPB2004 during double-blind treatment phase. A causal association of ALT elevations with JNJ-3989 has not been confirmed and the underlying mechanism for ALT elevations being more frequent in the context of HBV/HDV co-infection is not yet understood.

# Reproductive Risks and Pregnancy

In the EFD studies, JNJ-3989 was not teratogenic in rats and rabbits. The fertility in male and female rats is not impacted with JNJ-3989 up to a dose of 180 mg/kg/week.

Based on the difference in metabolic pathways and in vitro data indicating absence of impact of JNJ-3989 on CYP enzymes and transporters, no clinically relevant interactions are anticipated between JNJ-3989 and oral contraceptives.

### **Potential Genotoxicity**

JNJ-3989 is considered to be devoid of genotoxic activity. Nonclinical carcinogenicity studies have not been conducted.

## Other Potential Toxicity/Events of Special Interest

Hematologic abnormalities are an event of special interest for JNJ-3989 and JNJ-6379 based on animal studies (refer to 2.3.2.2.2 for further information).

JNJ-3989 is considered non-cytotoxic, did not activate human platelet aggregation, did not activate the innate immune system to a significant degree in vitro, and did not activate complement in vitro.

#### **Viral Resistance**

Treatment with JNJ-3989 may lead to viral resistance, but resistance to JNJ-3989 is not anticipated to impact treatment with other small interfering RNAs (siRNAs). Using these agents in combination, especially in combination with NAs, is expected to minimize the risk of emerging resistant viral variants.

### 2.3.2.2.2. Potential Risks for JNJ-6379

Since the initial protocol writing, interim results of the REEF-1 and REEF-2 studies had become available. The data suggested that JNJ-6379 has a negative impact on the HBsAg lowering effect of JNJ-3989+NA (see Section 2.2.2.1). In addition, there were new insights in the adverse renal profile of JNJ-6379 (see below). Taken together, it was concluded that JNJ-6379 had an unfavorable benefit-risk balance in combination with JNJ-3989+NA, compared to JNJ-3989+NA alone. Therefore, the Sponsor decided to discontinue treatment with JNJ-6379 in all ongoing

clinical studies effective immediately. For completeness, the potential risks for JNJ-6379 are still described in this section.

# Reproductive Risks and Pregnancy

In the fertility study in females, early embryonic development was affected: an increase in pre- and post-implantation loss, reduction in implantation and live fetuses at 300 mg eq./kg/day. The fetal loss seen during the early stages of pregnancy was considered the result of low hormone levels (decreased luteinizing hormone, progesterone, estradiol) induced by treatment with JNJ-6379.

In the EFD studies, JNJ-6379 was not teratogenic in rats and rabbits.

In the EFD study in rats, fetal weights at 300 mg eq./kg/day were lowered, and there was retarded ossification from 100 mg eq./kg/day onwards. The NOAEL for EFD was considered to be  $\frac{\text{CC}}{\text{CC}}$ . At this dose, the AUC0 24h was 84,000 ng.h/mL and the Cmax was 5,190 ng/mL.

In the EFD study in rabbits, the NOAEL for EFD was considered to be the highest dose tested, ie, At this dose, the AUC0 24h was 99,200 ng.h/mL and the Cmax was 6,880 ng/mL.

### **Potential Genotoxicity**

JNJ-6379 was not genotoxic in the in vitro and in vivo tests.

JNJ-6379 did not affect male or female fertility. Carcinogenicity studies are not yet conducted.

# Other Potential Toxicity/Events of Special Interest

Based on nonclinical findings in rats and dogs and based on clinical findings, increased cholesterol was identified as a laboratory abnormality of interest.

Renal complications are considered an event of special interest for JNJ-6379. Immediate treatment-emergent decrease in mean eGFRcr, which was initially observed in the JADE study, has also been observed in both JNJ-6379 treatment arms in the ongoing REEF-1 study. The eGFRcr values remained reduced during treatment, with a fast rebound after end of treatment. The eGFRcr decrease (calculated from serum creatinine) may be an anomaly due to JNJ-6379 possibly interfering with tubular excretion of creatinine via inhibition of MATE-1 transporter. This hypothesis was supported by the absence of a pattern of increased biomarkers of proximal tubulotoxicity (the beta-2-microglobulin/creatinine and the retinol binding protein/creatinine ratios), suggesting that the eGFRcr reduction was due to transporter inhibition at the level of creatinine excretion from the proximal tubule rather than renal toxicity.

Emerging data from the REEF-2 study confirmed the transient pattern of eGFRcr declines but, in addition, showed an increase of the beta-2-microglobulin/creatinine and the retinol binding protein/creatinine ratios in some participants when TDF was continued and combined with JNJ-6379+JNJ-3989. These new data are suggesting that JNJ-6379 in combination with TDF may contribute to renal tubulo-toxicity.

Hematologic abnormalities are considered an event of special interest for JNJ-3989 and JNJ-6369. Mild thrombocytopenia was observed in recently conducted non-clinical toxicology studies with the combination of JNJ-3989 and JNJ-6379. In addition, in a 3-month combination study with 80 rats, 1 rat developed pancytopenia related to bone marrow depletion after 23 days of dosing. Previously, in a 9-month dog study in 24 dogs treated with JNJ-6379 alone, pancytopenia which correlated with a marked increase in plasma cell-like cells in the bone marrow was observed in 1 dog after 60 days of dosing. Refer to Section 8.3.6.4. A minor additive effect was observed in vitro in human bone marrow derived erythroid and myeloid progenitors when combining JNJ-6379 and Peg-IFN-α2a.

### **Viral Resistance**

Treatment with JNJ-6379 may lead to emergence of viral variants with reduced susceptibility or resistance to JNJ-6379. Based on nonclinical data, these variants remain susceptible to tenofovir disoproxil and ETV but might affect treatment options with CAMs in the future. All 5 participants with virologic breakthrough in the Jade study who received 75 mg JNJ-6379 monotherapy, had an emerging core amino acid mutation T33N, which is known to confer reduced JNJ-6379 activity in vitro (see Section 2.2.1 for the results of the IAs).

# **Drug-drug Interactions**

Based on results from DDI study 56136379HPB1004 investigating the potential effect of coadministration of JNJ-6379 with oral contraceptives, it is not anticipated that the efficacy of oral contraceptives will be impacted during coadministration with JNJ-6379 since the exposure of a progestin sensitive to CYP3A4 induction was not significantly affected by coadministration of JNJ-6379. In contrast, it is anticipated that coadministration with ethinylestradiol-containing contraceptives will result in an increased exposure to ethinylestradiol. Therefore, specific requirements on the use of ethinylestradiol-containing contraceptives are included in Section 6.5, Concomitant Therapy.

# 2.3.2.2.3. Potential Risks for Tenofovir Disoproxil and PeglFN-α2a

For the general potential risks of tenofovir disoproxil and PegIFN- $\alpha$ 2a refer to the respective prescribing information and Summary of Product Characteristics.

Risks specific for this study design are listed below:

- PegIFN-α2a might increase the immunogenicity of JNJ-3989.
- Combination of PegIFN-α2a with JNJ-3989 and JNJ-6379 might increase the risk of hematologic abnormalities and/or of bone marrow suppression.
- JNJ-6379 might increase tenofovir plasma concentrations.

# 2.3.3. Benefit-Risk Assessment for Study Participation

Based on the available data and taking into account the measures taken to minimize risk to participants of this study, the potential risks identified in association with the study treatment are

justified by the anticipated benefits that may be afforded to participants with HBeAg positive chronic hepatitis B virus infection and normal ALT for the following reasons:

- At the time of protocol writing, JNJ-3989 was generally safe and well tolerated during the ongoing Phase 1 Study AROHBV1001 (see Section 2.2.2, Clinical Studies). All but one AE were mild or moderate in severity. All ISRs, identified as adverse drug reactions for JNJ-3989, were mild in intensity.
- No clinically significant safety concerns had been raised for JNJ-6379 at the time of initial protocol writing, based on the safety information from studies in healthy adult participants and adult participants with chronic HBV infection. Most observed AEs at that time were mild in severity and considered not related to JNJ-6379 by the investigator (see Section 2.2.2, Clinical Studies). At the time of Protocol Amendment 6 writing, it was concluded that JNJ-6379 has an unfavorable benefit-risk balance in combination with JNJ-3989+NA, compared to JNJ-3989+NA alone (see Section 2.3.2.2.2). Therefore, the Sponsor decided to discontinue treatment with JNJ-6379 in all ongoing clinical studies effective immediately, as a measure to minimize risk to participants of this and other studies.
- Events of Special Interest are significant AEs that are judged to be of special interest because of clinical importance, known class effects or based on nonclinical signals. Events of Special Interest that will be carefully monitored during the study, include ISRs, ALT/aspartate aminotransferase (AST) elevations, renal complications, hematologic abnormalities, and events related to cholesterol increase (Section 8.3.6, Adverse Events of Special Interest and Section 8.2.4, Clinical Safety Laboratory Assessments). In addition, the following toxicities will also be carefully monitored: rash and acute systemic allergic reactions (Section 8.3.7, Other Toxicities).
- Continued careful assessment of the safety, efficacy, and PK during treatment is included in this study.
- To minimize potential risk and stress to participants, the following measures are in place:

Utilization of selection criteria which exclude participants who may potentially be at higher risk of an AE (see Section 5, Study Population).

Utilization of withdrawal criteria (see Section 7, Discontinuation of Study Intervention and Participant Discontinuation/Withdrawal). If a participant drops out due to withdrawal of consent, he/she retains the option to participate in the safety follow-up procedures.

At regular time points throughout the study (see Schedule of Activities), blood samples for biochemistry, blood coagulation, and hematology and urine samples for urinalysis, urine chemistry, and renal biomarkers will be collected. Vital signs (systolic and diastolic blood pressure, pulse rate, and body temperature), height (only at screening), body weight, and electrocardiograms (ECGs) will be recorded throughout the study. Physical examinations will be performed and AEs will be assessed (see Section 8.2, Safety Assessments). Events of Special Interest and other toxicities will be closely monitored (Section 8.3.6, Adverse Events of Special Interest and Section 8.3.7, Other Toxicities).

Based on pre-clinical and clinical data available today, the combination of JNJ-3989, tenofovir disoproxil, and short-term PegIFN- $\alpha$ 2a is considered safe. Data from nonclinical combination toxicity studies (Section 2.2.1.3) showed a minimal additive effect on myeloid and erythroid cells in vitro when combining JNJ-6379 and PegIFN- $\alpha$ 2a

and confirmed that combination of PegIFN- $\alpha$ 2a with JNJ-3989 did not induce any synergistic or additive effect in monkeys up to 3 months of treatment. Review of 48-week hematology data from the ongoing Phase 2 clinical study REEF-1 (Section 2.2.2.1) did not identify any safety concerns.

The impact of PegIFN-α2a addition to JNJ-3989 on ALT elevations is not known. Strict rules for management of ALT elevation are in place (refer to Section 8.3.6.2, Intervention-emergent ALT/AST Elevations).

A Data Review Committee (DRC) will be established for continuous monitoring of SAEs, AEs leading to discontinuation, and ALT flares to ensure the continuing safety of the participants enrolled in the current study (see Section 9.6, Data Review Committee). In addition, an Independent Flare Expert Panel (IFLEP) will be appointed to characterize and adjudicate each ALT flare (see Section 9.7, Independent Flare Expert Panel).

After stopping treatment with JNJ-3989, JNJ-6379 (if applicable), PegIFN-α2a, and NA (if NA completion criteria are met at consolidation Week 12), participants will be monitored closely during the follow-up phase, with frequent follow-up visits and pre-defined NA re-treatment criteria in case of flares (Section 6.6.2, NA Re-treatment Criteria and Monitoring After Stopping of NA).

The post-treatment monitoring and NA re-treatment criteria were further updated based on findings from a case of post-treatment HBV reactivation with subacute hepatic failure and assessment of additional REEF-2 study data (Section 6.6.2).

JNJ-3989 will be administered using a proper subcutaneous technique to decrease the risk of ISRs. ISRs will be managed as outlined in Section 8.3.6, Adverse Events of Special Interest.

Any clinically significant abnormalities persisting at the end of the study/early discontinuation will be followed up by the investigator until resolution (return to baseline) or until stabilization (to be agreed upon with the sponsor).

		•	Time to achieve HBsAg seroclearance, HBeAg seroclearance, and/or HBV DNA <lloq.< th=""></lloq.<>
		•	Proportion of participants with HBeAg, HBsAg, and HBV DNA levels and/or changes from baseline below/above different cut-offs.
•	To evaluate the frequency of virologic breakthrough.	•	Proportion of participants with virologic breakthrough.
•	To evaluate the efficacy of NA re-treatment in participants who meet the criteria for NA re-treatment.	•	Proportion of participants who reach HBV DNA undetectability after re-start of NA treatment during follow-up.
•	To evaluate the PK of JNJ-3989 (ie, JNJ-3976 and JNJ-3924) and optionally of JNJ-6379, NA and/or PegIFN-α2a.	•	PK parameters of JNJ-3976 and JNJ-3924.

CONFIDENTIAL – FOIA Exemptions Apply in U.S.

Objectives	Endpoints		
	Optionally, PK parameters of JNJ-6379, NA and/or PegIFN-α2a compared to historical data.		
Exploratory			
To identify baseline and on-treatment markers associated with efficacy.	
 
Association of baseline characteristics and baseline/on-treatment viral blood markers (such as age, and baseline/on-treatment HBsAg levels) with selected efficacy variables.
 
		
To explore changes in the severity of liver disease.	Changes in fibrosis (according to Fibroscan liver stiffness measurements) at end-of-study intervention (EOSI) and end of follow-up versus baseline.		
To explore efficacy of the study intervention in terms of changes in HBV RNA and HBcrAg levels.	Changes from baseline in HBV RNA and HBcrAg levels during the study intervention and follow-up.		
To explore the impact of study intervention on participants' physical and emotional functioning, and health-related quality of life using patient-reported outcomes (PROs) during study intervention and follow-up.	
 
Changes over time in score on the Short Form 36 version 2 (SF-36v2).
 
Changes over time in score on the Hepatitis B Quality of Life (HBQOL) Instrument.
 
Changes over time in the 5-Level EuroQol 5-Dimension (EQ-5D-5L) Visual Analog Scale (VAS) score and Index score.
 
Changes over time on the Patient Global Impression of Change (PGIC).
 
		
• To explore the relationship between plasma PK parameters (JNJ-3976, JNJ-3924, and optionally JNJ-6379, NA and/or PegIFN-α2a) and selected pharmacodynamic (PD) parameters of efficacy and/or safety, as applicable.	• Relationship between various plasma PK parameters (JNJ-3976, JNJ-3924, and optionally JNJ-6379, NA and/or PegIFN-α2a) and selected efficacy and/or safety endpoints, as applicable.		
• To explore the effect of PegIFN-α2a coadministration on the PK of JNJ-3989 (optional PK substudy).	Effect of PegIFN-α2a coadministration on the PK of JNJ-3976 and JNJ-3924.		
To explore the HBV genome sequence during study intervention and follow-up.	Assessment of intervention-associated mutations.		
To explore HBV-specific T-cell responses during study intervention and follow-up.*	Changes from baseline in HBV-specific peripheral blood T-cell responses.		

\* Peripheral blood mononuclear cell (PBMC) samples for immune analyses will be collected at selected sites only.

Refer to Section 8, Study Assessments and Procedures for evaluations related to endpoints.

For the definitions of terms, refer to Section 10.1, Appendix 1, Abbreviations and Definitions of Terms.

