## 7.2. Definitions

(Baseline) Genetic variations (i.e., aka baseline polymorphisms) are defined as changes (on the amino acid or nucleotide level) in the subject viral sequence compared to a HBV genotype specific reference viral sequence and/or the universal HBV reference sequence (NCBI ID X02763). The reference sequence to be used is provided in the database. The reference viral sequences to be used are:

Virus	Genotype	NCBI genbank accession	NGS isolate name	Sanger genbank accession	Sanger isolate name
HBV	A	X02763	adw2	X02763	adw2
HBV	B	AB219428	PNN3	D00329	pJDW233
HBV	C	GQ924620	M38	AB014362	03D03HCC
HBV	D	AF121240	11066	V01460	ayw
HBV	E	AB106564	GA325	X75657	ayw4
HBV	F	AY090458	70H	X75658	adw4q

Virus	Genotype	NCBI genbank accession	NGS isolate name	Sanger genbank accession	Sanger isolate name
HBV	G	AF160501	IG29227	AB064311	USG825
HBV	H	FJ356716	CL150171	AY090460	LAS2523
HBV	I	EU833891	H4536-07		

**Wild type:** If at certain position the amino acid/nucleotide in the subject sequence matches the reference sequence, that is no genetic variation is present at that position, the virus is considered to be wild type at that position.

**Emerging viral variation:** If at certain position a genetic variation is absent at baseline but present at later time point, the genetic variation is considered to be emerging at that time point. For NGS, emerging will be defined based on the frequency of variant at baseline and at the later time point. “Absent at baseline” is defined as a frequency of variant below 1% (<1%). “Present at later point” is defined as a frequency of variant equal or greater than 15% ( $\geq 15\%$ ) at the later time point.

**Enriched genetic variations:** are exclusively defined for NGS analysis. If at a certain position a genetic variation has a frequency of variant of  $\geq 1\%$  but  $< 15\%$  at baseline and a frequency of variant of  $\geq 15\%$  at a later time point and an increase in read frequency of  $\geq 15\%$ .

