All NGS data will be collected using a nt and aa read frequency cut-off of  $\geq 0.01$ . For the analysis of baseline nt changes and/or aa substitutions in terms of frequency of variant and impact on treatment outcome, a read frequency cut-off of  $\geq 0.15$  will be used. The analysis of treatment-emergent nt changes or aa substitutions will consider nt changes or aa substitutions absent at baseline ( $<0.01$  read frequency) but present at a read frequency of  $\geq 0.15$  at later time points. Virology analyses based on NGS data will also evaluate treatment-enriched nt changes and aa substitutions, defined as present at baseline with a read frequency  $\geq 0.01$  but  $<0.15$  and with an increase in read frequency of at least 0.15 post-baseline. A minimum increase in read frequency of 0.15 compared to baseline excludes small, potentially technical variations in the read frequency of minority nt changes and aa substitutions which are not expected to have clinical relevance. In addition, for subjects with treatment failure nt changes and aa substitutions detected with a read frequency  $\geq 0.01$  at baseline, at time of failure and at end of study will be described in a listing. The persistence of treatment-emergent nt changes and aa substitutions will be evaluated using a cut-off of  $\geq 0.15$  and  $\geq 0.01$ .

The applicability of the sequencing approach described here (e.g., the 0.01 sensitivity limit) will be assessed during the development program and might be adapted if needed.

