The return to baseline for subjects who meet re-treatment criteria during follow-up and treatment-emergent genetic variations at time of meeting the re-treatment criteria may be tabulated in frequency outputs based on NGS data, as well as the treatment-emergent genetic variations in subjects who did not return to baseline.

- Other Post-Baseline

The frequency of variant of genetic variations at other time points will be tabulated in frequency outputs (n, %), based on NGS data (1% and 15% cut-off), and the genetic variations will be listed for all subjects. Time points of specific interest are end-of-treatment, time point of re-treatment, and end-of-study.

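### SAP 7.2 and 7.3 cap treatment-enriched variants at under 15% at baseline, so a large on-treatment rise from 15% or more is not counted in any incidence table

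*Protocol*

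**What the plan says.** Protocol Section 3 lists HBV genome sequencing as exploratory, with the endpoint "Assessment of intervention-associated mutations". Section 2.3.2.2.1 states that "Treatment with JNJ-3989 may lead to viral resistance"; it adds that using the agents in combination, especially with NAs, is expected to limit that risk. Section 9.4.1.3 promises that relevant changes in the viral genome will be tabulated and described.

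SAP Section 7.2 sets the classes for next-generation sequencing (NGS) data. *Emerging* requires a frequency under 1% at baseline, and presence at the later time point "is defined as a frequency of variant equal or greater than 15" per cent. *Enriched* requires at least 1% but under 15% at baseline, at least 15% later, and a rise of at least 15%. Section 7.3 repeats the enriched rule on the 0-to-1 scale: the same baseline band, "with an increase in read frequency of at least 0.15 post-baseline". Its reason for the minimum rise is to keep out small shifts in minority variants that may be technical.

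SAP Section 7.5.2 tabulates the incidence of emergent and enriched variants at virologic breakthrough, at end of treatment in participants not meeting the NA completion criteria, at virologic or clinical flare, and at NA re-treatment. Section 7.3 does the same for the core, polymerase and JNJ-3989 binding-site positions. At other post-baseline time points, variants are tabulated "based on NGS data (1% and 15% cut-off), and the genetic variations will be listed for all subjects".

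**The concern.** The endpoint is about mutations associated with the intervention, so the informative quantity is change on treatment. The two classes that capture change both stop at a baseline frequency of 15%. A resident variant that goes from a minority or even mixture to near-complete dominance during treatment is the kind of change a reader would expect an incidence table to show. Under these rules it is not counted there. The prevalence tables cannot fill the gap, because the variant passes both cut-offs before and after treatment. At stake is whether the tabulated summary of on-treatment change at the positions of interest is complete.

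**Working it through.** **Inputs.** The emerging and enriched rules are from SAP 7.2, the restated enriched rule from SAP 7.3, and the 1% and 15% prevalence cut-offs from SAP 7.5.1 and 7.5.2. Write b for the baseline frequency and l for the later one.

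- Emerging: b < 0.01 and l ≥ 0.15.
- Enriched, SAP 7.2: 0.01 ≤ b < 0.15, l ≥ 0.15 and l − b ≥ 0.15.
- Enriched, SAP 7.3: 0.01 ≤ b < 0.15 and l − b ≥ 0.15.

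The rise is read as absolute percentage points, as the 0.15 in Section 7.3 implies.

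**Do the two sections agree?** Yes. With b ≥ 0.01 and a rise of at least 0.15, l is at least 0.01 + 0.15 = 0.16, so the extra l ≥ 0.15 condition in 7.2 never bites. A 0.001-step grid over all pairs found no disagreement.

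**Applying the rules:**

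| Baseline → later | Rise (points) | Class | Present at ≥15%, before / after |
|---|---|---|---|
| 0.5% → 95% | 94.5 | emerging | no / yes |
| 5% → 95% | 90 | enriched | no / yes |
| 14% → 29% | 15 | enriched | no / yes |
| 14.9% → 95% | 80.1 | enriched | no / yes |
| 15% → 95% | 80 | neither | yes / yes |
| 20% → 95% | 75 | neither | yes / yes |
| 50% → 95% | 45 | neither | yes / yes |
| 85% → 100% | 15 | neither | yes / yes |
| 86% → 100% | 14 | neither | yes / yes |
| 20% → 30% | 10 | neither | yes / yes |

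**Extent of the gap.** A rise of 0.15 is possible only if b + 0.15 ≤ 1, that is b ≤ 0.85. The unclassified zone is therefore every rise of at least 0.15 from a baseline of 0.15 to 0.85. The last two rows fall short of the 0.15 minimum, so they are left out by the floor on the rise and not by the ceiling on baseline.

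**Effect on the prevalence tables.** A 20% → 95% variant counts as present at both cut-offs at both times. Its contribution to any change in the counts is 1 − 1 = 0, although its frequency rose by 75 points.

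**Check of the proposed stratum.** Keeping l − b ≥ 0.15 and removing the upper limit on b classifies 15% → 95%, 20% → 95%, 50% → 95% and 85% → 100%. It leaves 20% → 30% and 86% → 100% unclassified, and no pair already classified changes class.

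**The case against.** The strongest reply is that the ceiling follows from the SAP's own scheme. Section 7.3 separately uses a 0.15 cut-off for analysing baseline changes and their effect on outcome, so a variant at 15% or more is treated as a baseline polymorphism, and enrichment describes minority variants that cross that line. This is a coherent taxonomy and the documents do not contradict themselves. It still leaves a question unanswered: relating outcome to the presence of a baseline variant (Section 7.5.1) does not show whether treatment raised that variant.

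A second reply is that little is hidden, and it largely stands. A reader might infer that such a variant disappears from the resistance reporting; it does not. Section 7.3 tabulates participants with a substitution at a position, a specific substitution or a profile, without restriction to emergent or enriched. Sections 7.5.1 and 7.5.2 tabulate prevalence at baseline and later. Variants are listed for participants with paired data at each event, for treatment failures at a read frequency of at least 0.01 (Section 7.3), and for all participants over the study (Section 7.5.3). The SAP does not say, however, that the listings show read frequencies over time, and a listing is not a count.

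A reader might also infer that the reported rate of intervention-associated substitutions is biased downward. Neither document defines a rate that includes further rises from 15% or more; the tables count exactly what they name. Nor do the documents support saying that variants at these baseline levels become dominant soonest.

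**Conclusion.** The point holds in a narrow form. Rises of at least 15 points from a baseline of 15% to 85% are in neither class, are not counted in the emergent/enriched incidence tables, and change no prevalence count. The stated rationale supports a minimum rise; it gives no reason for a maximum baseline, and a 75-point rise is not small technical variation.

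The size is minor. The endpoint is exploratory and descriptive, there is no formal hypothesis, and the primary endpoint is untouched. The target is about 60 participants, sequencing may be triggered by the sponsor virologist within assay limits, and Section 7.5 produces frequency outputs only when at least 5 participants have the relevant sequences. The documents do not say how many participants have a variant in this range at a position of interest; it could be none. The SAP's Amendment 4 log also reports only one participant who met the NA completion criteria and stopped NA at Consolidation Week 12. If that is the full off-treatment group, the flare and re-treatment tables may not be produced, and the breakthrough and end-of-treatment tables are where the gap would matter.

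**What to change.** In SAP Sections 7.2 and 7.3, add a separately reported stratum: baseline read frequency of at least 0.15 with a post-baseline rise of at least 0.15. Keep the present enriched class (1% to under 15% at baseline) unchanged, so that existing counts remain comparable. Include the new stratum as its own row in the Section 7.3 tables for core, polymerase and JNJ-3989 binding-site positions, and in the Section 7.5.2 incidence tables. If the ceiling is deliberate, give the reason and state that the incidence tables leave out further rises in variants already at 15% or more.

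The cost is a short wording change and one extra derivation. Section 7.3 already collects read frequencies from 0.01 upwards and allows the sequencing approach to be adapted, so no new data are needed. The drawback is that the total of reported treatment-associated variants may come out slightly higher.
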